## **5.9 Discontinuation of Study Intervention and Participant Discontinuation/Withdrawal**

For participants randomized to apixaban who develop a thrombotic or major bleeding event, the study investigator or designee will decide whether the participant should continue with apixaban, temporarily pause apixaban, or return to standard warfarin therapy. Such decisions are at the discretion of the participant's treating clinician. Participants who are returned to warfarin (section 5.8) or stop anticoagulation, regardless of whether or not they have either a thrombotic or major bleeding event, will continue to be followed in the study.

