### 1.2 Study Design

This is a prospective, multicenter, open-label, randomized, active controlled clinical trial to determine if patients with an On-X aortic valve, alone or as an On-X Ascending Aortic Prosthesis, can be maintained safely and effectively on apixaban. The primary outcome is a composite rate of valve thrombosis and valve-related thromboembolism, which will be used for co-primary analyses. The first co-primary analysis will determine whether apixaban is non-inferior to warfarin (INR target range 2.0 - 3.0) in patients with an On-X mechanical heart valve implanted in the aortic position. The second co-primary analysis will compare the composite rate for apixaban-treated patients to updated OPC for FDA-approved mechanical heart valves in the aortic position. Each patient will be followed for at least 2 years and each randomized arm will achieve at least 800 pt-yrs.

The study will consist of approximately 1000 patients (randomized 1:1 with approximately 500 patients in the apixaban arm and 500 patients in the warfarin arm) at a minimum of 3 sites and up to 60 sites in North America, and potentially in Europe and/or Japan, who are 18 years of age or older, at least 3 months out from an On-X aortic valve implantation, and currently managing their anticoagulation with warfarin.

Patients will be randomized to either continue warfarin or switch to apixaban. Patients randomized to apixaban will receive 5 mg twice daily (BID), or apixaban 2.5 mg BID in patients with 2 or 3 of the following characteristics:

- age  $\geq$  80 years
- weight  $\leq$  60 kilograms
- creatinine  $\geq$  1.5 mg/dL (133 micromol/L)

For patients randomized to apixaban, INR testing will be performed on the current warfarin dose with the following algorithm to initiate apixaban:

1. INR  $<$  2; stop warfarin and start apixaban

2. INR 2.0 to 3.0; hold warfarin for 2 days, start apixaban on day 3
3. INR > 3.0 to 4.0; hold warfarin for 4 days, start apixaban on day 5
4. INR > 4.0; hold warfarin for 2 days, recheck INR, refer to steps 1, 2, or 3

The procedures to be performed throughout the study are outlined in the Schedule of Activities in the study protocol (see Section 1.1 of the study protocol).

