### **Intent-to-treat (ITT)**

All patients who are randomly assigned to study intervention, regardless of treatment discontinuation or switching, will be included in the intent-to-treat (ITT) population.

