## 6.3 Efficacy Analysis

### 6.3.1 Primary Efficacy Variable

The co-primary analysis will be conducted for the primary efficacy outcome using the ITT population.

A linearized event rate per arm is defined as the total number of patients with adjudicated efficacy outcomes divided by the total patient time (years). The approximate 95% CI for the difference of linearized event rates will be calculated as

$$\left( \frac{r_A}{T_A} - \frac{r_W}{T_W} \right) \pm 1.96 \sqrt{\frac{r_A}{T_A^2} + \frac{r_W}{T_W^2}},$$

where subscript A and W denote the apixaban and warfarin arms, respectively, and r is the total number patients with adjudicated efficacy outcomes, and T is the total patient time (years). (Liu et al. 2006)

As the first co-primary analysis, if the upper bound of the 95% CI for the difference of linearized event rates is less than the non-inferiority margin of 0.0175/pt-yr (=1.75%/pt-yr), it will be concluded that apixaban is non-inferior to warfarin for the primary efficacy outcome in patients with an On-X mechanical heart valve implanted in the aortic position.

As the second co-primary analysis, if the apixaban arm achieves at least 800 pt-yrs and the linearized event rate is less than two times the OPC or 0.034/pt-yr (=3.4%/pt-yr), the OPC test is passed. (Wu et al., 2014)

Once both co-primary analyses are met using the ITT population, we declare success and that apixaban is a reasonable alternative to warfarin for thromboembolic event prevention in this population.

If a non-inferiority for the primary efficacy outcome is established, a superiority test for the primary efficacy outcome will be performed using the ITT population. If the upper bound of the 95% CI for the difference of linearized event rates is less than zero, it will be concluded that apixaban is superior to warfarin for the primary efficacy outcome in patients with an On-X mechanical heart valve implanted in the aortic position.

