## 6.8 Sensitivity Analysis

Three sensitivity analyses are planned for the non-inferiority hypothesis of the primary efficacy outcome – using the NI margin of 1.75%/pt-yr and the OT population, using the NI margin of 1.75%/pt-yr and the AT population, and using a Cox proportional hazard regression model with a hazard ratio of 2 for the NI margin and the ITT population.

For the sensitivity analysis using a Cox proportional hazard regression model, the proportional hazards assumption will be assessed and time from the randomization date to the date of first adjudicated primary composite outcome or censoring will be determined as specified in Section 6.1.6. As mentioned in Section 6.1.6, a sensitivity analysis will be done for all three analysis populations with the more conservative censoring date where all elements of the primary composite outcome were assessed.

The superiority hypothesis for the primary safety outcome will be tested using the ITT and OT populations as sensitivity analyses. Time to the date of first adjudicated major bleeding or censoring will be determined as specified in Section 6.1.6.

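### The OPC co-primary is described as a test in apixaban-treated patients but is calculated only on ITT time, and no planned analysis applies the 3.4%/pt-yr rule to time on apixaban

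*Combined protocol and SAP*

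**What the plan says.** - **Purpose.** SAP v1.4 section 1.2 (Study Design): "The second co-primary analysis will compare the composite rate for apixaban-treated patients to updated OPC". The protocol uses the same idea in sections 2 and 4.1.
- **Population tested.** SAP v1.4 section 6.3.1: "The co-primary analysis will be conducted for the primary efficacy outcome using the ITT population". Section 2 defines it: "All patients who are randomly assigned to study intervention, regardless of treatment discontinuation or switching, will be included in the intent-to-treat (ITT) population".
- **Rule.** The test is met "if the apixaban arm achieves at least 800 pt-yrs and the linearized event rate is less than two times the OPC"; the limit is 3.4%/pt-yr. Protocol 8.2 states that this test carries no significance level, so it is a rule on the point estimate.
- **After stopping apixaban.** Protocol 5.9: "Participants who are returned to warfarin (section 5.8) or stop anticoagulation", whatever the reason, "will continue to be followed in the study". SAP v1.4 section 6.1.6 censors ITT follow-up at last relevant contact or death, not at drug stop.
- **Sensitivity analyses.** SAP v1.4 section 6.8: "Three sensitivity analyses are planned for the non-inferiority hypothesis of the primary efficacy outcome". They use OT, AT and a Cox model. Neither that section nor protocol 8.4.3 mentions the OPC test.

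**The concern.** The second co-primary asks whether apixaban gives acceptable anticoagulation against a fixed external figure. The calculation answers a related question, about patients assigned to apixaban whatever they later took. Once a participant returns to warfarin, further time enters the denominator, further events enter the numerator, and the time counts toward the 800 pt-yr. If events are less frequent on warfarin than on apixaban, the ITT rate lies below the on-apixaban rate. With no confidence bound in the rule, nothing absorbs that shift.

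At stake is one of the two conditions for declaring success, and success is meant to support a change to the valve's label. As planned, the report need not show whether an OPC pass also holds on apixaban exposure, or how much of the 800 pt-yr was spent on apixaban.

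**Working it through.** **Inputs.** OPC limit 3.4%/pt-yr and 800 pt-yr (SAP v1.4, 6.3.1). Warfarin rate w = 1.75%/pt-yr, 95% CI 1.09 to 2.81 (protocol 8.2). Margin 1.75%/pt-yr, one-sided 2.5%, 1-year accrual with half enrolled by 40% of that time, minimum 2 years of follow-up, loss hazard 0.026 (protocol 8.2). The off-apixaban share f of arm time is not in the documents; 5% to 20% is assumed below.

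**The plan's own figure.** Truncated-exponential accrual with these inputs gives 2.428 pt-yr per participant. Then n per arm = 2 × (0.0175/2.428) × (3.2415/0.0175)² = 494.6, so N = 990, as stated. With 500 per arm, exposure is 500 × 2.428 = 1,214 pt-yr, SE = √(2 × 0.0175/1,214) = 0.00537, and power = Φ(0.0175/0.00537 − 1.96) = 90.3%, as in SAP Table 1. The checks below use 1,214 pt-yr per arm.

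**Dilution.** ITT rate = (1 − f)x + f·w, where x is the on-apixaban rate. Setting this to 3.4 gives x = (3.4 − f·w)/(1 − f).

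| f | w = 1.09 | w = 1.75 | w = 2.81 |
|---|---|---|---|
| 5% | 3.52 | 3.49 | 3.43 |
| 10% | 3.66 | 3.58 | 3.47 |
| 20% | 3.98 | 3.81 | 3.55 |

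**Patient-years.** At exactly 800 ITT pt-yr, f = 20% leaves 0.8 × 800 = 640 pt-yr on apixaban. At the planned 1,214, on-apixaban time stays at or above 800 until f reaches 1 − 800/1,214 = 34%.

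**OPC test alone, x = 4.0, w = 1.75.** 0.034 × 1,214 = 41.3, so up to 41 events pass.
- No crossover: Poisson mean 48.6, P(pass) = 16%.
- f = 10%: ITT rate 3.775%, P(pass) = 27%.
- f = 20%: ITT rate 0.8 × 4.0 + 0.2 × 1.75 = 3.55%, mean 43.1, P(pass) = 41%.
- f = 20% on apixaban time only: 971 pt-yr, up to 33 events pass, mean 38.8, P(pass) = 20%.

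**Both co-primaries, x = 4.0.** Events are independent Poisson, with no crossover in the warfarin arm. Non-inferiority uses the section 6.3.1 interval, and w also applies to post-switch time.

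| w | f | OPC pass | Both pass |
|---|---|---|---|
| 1.75 | 0 | 16% | 0.4% |
| 1.75 | 10% | 27% | 1.0% |
| 1.75 | 20% | 41% | 2.4% |
| 2.81 | 0 | 16% | 8% |
| 2.81 | 20% | 27% | 15% |

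At w = 1.75, non-inferiority alone passes 0.4% and 2.4% of the time at f = 0 and 20%. It is the binding test there, and it is diluted too. For scale, 41 apixaban events in 1,214 pt-yr need at least 38 warfarin events (3.13%/pt-yr) for non-inferiority: (41 − 38)/1,214 + 1.96 × √79/1,214 = 1.68%, below 1.75%.

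**The case against.** **The crossover share may be small.** Protocol 5.9.1 describes permanent discontinuation as rare. At 5% the limit moves only from 3.40 to 3.49. This stands: 10% and 20% are illustrations, not forecasts.

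**Follow-up after stopping may be short.** SAP v1.4 section 6.1.3 redefines the end of study by reference to 30 days after the last dose. If that caps everyone, off-drug time is at most 500 × 30/365.25 = 41 pt-yr, which is 5.1% of 800, and the limit is again about 3.49. Section 6.1.6 states no such cap for ITT, so the point is unresolved. The SAP also does not say whether patient time ends at the first event; if it does, people who switch because of a primary event add no warfarin time.

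**The direction is not guaranteed.** Some participants stop all anticoagulation. Their rate could exceed the on-apixaban rate and raise the ITT figure.

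**OT has its own bias.** A 7-day cut-off drops later events and censors informatively, which can flatter apixaban. This stands, and is why ITT should remain primary.

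**The OT rate will exist anyway**, through the OT non-inferiority analysis. That is so, but no OPC criterion is attached to it.

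A reader might infer that ITT serves no purpose in a one-arm test, or that crossover would let a clearly unacceptable rate be declared a success. The documents support neither. ITT keeps post-discontinuation events in view, success also requires non-inferiority, and a 4.0% rate passes the OPC rule 16% of the time with no crossover because the rule is a point estimate.

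**Conclusion.** The concern holds as a gap between the stated comparison and the planned calculation. The OPC test is presented as one in apixaban-treated patients, is run only on ITT time, and is not repeated on apixaban exposure.

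The size is modest and conditional. If post-switch time runs at 1.75%/pt-yr, the on-apixaban rate equivalent to an ITT rate of 3.4% is somewhat above the limit and depends on the assumed share: 3.49 to 3.81 for 5% to 20%, and 3.55 to 3.98 at 20% across the protocol's interval for warfarin. The effect on the overall declaration is small at the planned warfarin rate and larger at a high one. A high warfarin rate is also where the OPC test matters most: SAP section 6.1.8 gives uncertainty about that rate as the reason for having both tests.

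The larger changes in the OPC pass probability taken alone, such as 16% to 41%, should not be read as the risk of a wrong final conclusion. The mechanism is certain from the text; its size is not.

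**What to change.** - Keep ITT as the primary OPC test in section 6.3.1.
- In section 6.8, add a prespecified OT sensitivity analysis for the OPC test. It should apply the 3.4%/pt-yr rule to apixaban events and time from first dose to 7 days after permanent discontinuation, and report on-apixaban patient-years against 800.
- State in advance that an ITT pass with an OT failure will be interpreted as not robust.
- Do not use AT for this. Section 2 keeps a participant who switched to warfarin after one apixaban dose in the apixaban arm, and AT censoring in 6.1.6 does not stop at discontinuation, so post-switch time remains.
- Reconcile the 30-day end-of-study wording in 6.1.3 with the ITT censoring rule in 6.1.6.
- Section 6.1.3 of v1.4 records that the trial was stopped, so date the addition and label it as made after the stop.

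Cost: SAP wording and one more reported rate from data the OT non-inferiority analysis already needs. The downside is a possibly less favourable OPC result. Requiring a pass on both bases would be stricter, but it is a trade-off given the OT bias and is not needed to close the gap.

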### 6.3.2 Secondary Efficacy Variables

For the individual components of the primary efficacy outcome as secondary outcomes, a linearized event rate for each treatment group will be calculated as percentage per patient year, and the 95% CI for the difference of linearized event rates will be estimated as Section 6.3.1 above. The ITT population will be used, and statistical testing will be considered exploratory.

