## 11 References for sample size calculation

**Table 3. References used to estimate the primary outcome rate of warfarin (%/pt-yr).**

Author	Chambers	McNicholas	On-X Original PMA# P000037	PROACT		Tossios	Wu
				High Risk Control	Low Risk Control		
Year	2013	2006	2001	2018		2007	2006
Country	UK, Spain, Greece	USA	Germany, Spain, Greece	US, Canada		Germany	South Africa
Sample size	214	142	184	190	102	264	104
% of total	18%	12%	15%	16%	9%	22%	9%
Mean patient age (yrs)	59.7	58.6	60.2	55.8	52.5	62	39.7
Median Follow-up (yrs)	5.5	4.5*	2.2*	5.7	3.4	3.9	1.8*
Total Follow-up (pt-yr)	1360	659	411.8	1090	343.5	1069.4	172.5
Target INR	2.0-3.0	2.5-3.5	SoC	2.0-3.0	2.0-3.0	2.5-3.5	1.5-2.5
Mean INR	NR	NR	NR	2.5	NR	NR	43% out of range
NR = Not Reported in the manuscript; * Mean follow-up (yrs) was reported;							
Number of events							
- TE †	8	6	7	19	1	16	2
- Thrombosis	0	0	0	2	0	0	0
- VRM	7	5	1	7	4	19	7
- % TEs in VRM	NR	NR	NR	NR	NR	26% §	NR
Total number of events with 26% reduction to VRM for TE overlap (r)§	13.2	9.7	7.7	30.1 #		30.1	7.2
Linearized event rate with 26% Reduction to VRM for TE overlap (<math>\lambda</math>)§	0.97%	1.47%	1.88%	2.10% #		2.81%	4.16%
Standard error of linearized event rate‡	0.0027	0.0047	0.0068	0.0038		0.0051	0.0155

† Peripheral TE was included if provided; § A 26% VRM was assumed to be related to TE event; # calculated by summing up numbers of events and follow-up years from both high and low risk controls; ‡ calculated as  $\lambda/\sqrt{r}$

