#### 1.1.3 Secondary Efficacy Objectives

- To determine if apixaban is superior to warfarin (INR target range 2.0 - 3.0) for the primary composite outcome of valve thrombosis and valve-related thromboembolism in patients with an On-X mechanical heart valve implanted in the aortic position

- To compare apixaban with warfarin (INR target range 2.0 – 3.0) for the individual components of the primary outcome (valve thrombosis and valve-related thromboembolism) in patients with an On-X mechanical heart valve implanted in the aortic position
- To compare apixaban with warfarin (INR target range 2.0 - 3.0) for the primary composite outcome of valve thrombosis and valve-related thromboembolism in pre-specified subgroups of patients with an On-X mechanical heart valve implanted in the aortic position

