### 5.2 Secondary Safety Outcome

All secondary bleeding definitions and clinical outcomes defined in Section 7 of the study protocol, including valve thrombosis or dysfunction, stroke or TIA, myocardial infarction, arterial thromboembolism, bleeding, hospitalization and the reason for hospitalization, death and the cause of death, will be collected and be summarized with frequencies and percentages per treatment group.

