A baseline value is defined as the most recent assessment taken prior to/on day of randomization. When there is a missing assessment, it will not be imputed, thus, patients are excluded from any changes from baseline analysis for which they have a missing baseline value.

Due to the anticipated small number of events, stratification by site would produce sparse data and therefore, the baseline hazard within each stratum would be poorly estimated with such models. For this reason, sites will be pooled together and all Cox proportional hazards models will be adjusted for age of valve only.

Unless otherwise specified, all Kaplan-Meier rates and Kaplan-Meier curves will be performed only with the treatment group.

Case report form (CRF) data collected will be presented within data listings. The data listings will be sorted by treatment group, site number, patient number and visit.

The treatment label for all Tables, Listings and Figures will be:

Treatment	Treatment Label for TFLs
Apixaban (5 mg BID or 2.5 mg BID)	Apixaban
Warfarin (INR target range 2.0 - 3.0)	Warfarin
All Treatments	All Patients

Should any of the statistical methods proposed prove unsuitable during the final analysis, more appropriate methods will be used, and any changes will be documented in the clinical study report (CSR), including the rationale for use. These include the transformation of the data (for example to a logarithmic scale) in order to satisfy the model assumptions such as normally distributed residuals with constant variance; or the application of non-parametric techniques.

Additional ad-hoc analyses may be conducted as deemed appropriate.

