### 6.4.2 Secondary Safety Variables

All secondary bleeding definitions and clinical events cases defined in Section 7 of the study protocol will be summarized with frequencies and percentages per treatment group using the AT population.

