## 6.7 Subgroup Analysis

Subgroup analyses for the primary efficacy outcome will be performed by the following factors at baseline (Day 1 Randomization).

- Age: ≤ 65 years vs. > 65 years
- Race: white vs. non-white
- Sex: female vs. male
- Conduit type: valve alone vs. valve in a conduit
- Baseline apixaban dose: 5 mg BID vs. 2.5 mg BID
- Time from surgery: ≤ 1 year vs. > 1 year
- Valve size (mm): ≤ 21 mm vs. > 21 mm

An additional analysis will be done comparing outcomes by post-randomization TTR in the warfarin arm as <50%, 50-69%, and ≥ 70%. Details of this analysis will be described in a supplementary analysis plan.

There are no guideline or consensus definitions of aortic valve replacement patients who are at high risk of valve thrombosis or valve-related thromboembolism. An additional subgroup analysis will stratify based on the high-risk criteria utilized in the original PROACT trial (Puskas et al., 2018) with high-risk patients defined as having any of the following: atrial fibrillation, left ventricular ejection fraction < 30%, left atrial dimension >50mm, significant vascular disease, and history of neurological events within 1 year.

For each subgroup factor, the linearized event rates of the primary efficacy outcome for both treatment groups and the 95% CI for the difference of linearized event rates will be estimated as Section 6.3.1 above. The ITT population will be used, and statistical testing will be considered exploratory.

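### The Wald interval that SAP v1.4 section 6.3.2 reuses for valve thrombosis breaks down at very low counts: 0 v 0 events gives a 95% CI of exactly [0, 0]

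*Combined protocol and SAP*

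**What the plan says.** Comparing the arms on each component is a secondary objective in SAP v1.4 section 1.1.3: "for the individual components of the primary outcome (valve thrombosis and valve-related thromboembolism) in patients with an On-X mechanical heart valve". Section 6.3.2 gives the method by cross-reference: "the 95% CI for the difference of linearized event rates will be estimated as Section 6.3.1 above". Section 6.7 carries the same cross-reference for subgroups: "For each subgroup factor, the linearized event rates of the primary efficacy outcome for both treatment groups" are reported with that interval.

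Section 6.3.1 introduces the formula with "The approximate 95% CI for the difference of linearized event rates will be calculated as". It is the difference of the two rates plus or minus 1.96 times the square root of rA/TA² + rW/TW², where r counts patients with an event and T is patient-years.

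No section states a rule for zero or very small counts, and no score or exact interval for a rate difference appears in the documents. The only fallback is general, in 6.1.1: "Should any of the statistical methods proposed prove unsuitable during the final analysis, more appropriate methods will be used". Sections 6.3.2 and 6.7 both label their testing exploratory.

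**The concern.** The Wald variance is built from the observed counts alone. An arm with no events contributes no variance, so the interval claims certainty about that arm. Two empty arms give a zero-width interval.

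Valve thrombosis is the component exposed to this. It is one of only two, and the protocol's Table 3 ("References used to estimate the primary outcome rate of warfarin (%/pt-yr") lists two thromboses in all its columns together. A reader would use the interval to see how large an excess of thrombosis on apixaban the trial can exclude. At 0 v 0 or 1 v 0 the planned interval answers that too optimistically.

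**Working it through.** **1. The plan's own figure.** Inputs from SAP 6.1.8: 1.75%/pt-yr in both arms, margin 1.75%/pt-yr, one-sided alpha 2.5%, power 90%, accrual over 1 year with half enrolled by 0.4 year, minimum follow-up 2 years, loss hazard 0.026. Truncated-exponential accrual gives a mean patient-time of 2.428 years. Then n per arm = 2 × (0.0175/2.428) × (1.960 + 1.282)² / 0.0175² = 494.6, so N = 990, as stated. With 500 per arm the planned exposure is 500 × 2.428 = 1,214 pt-yr. Results below are for 1,214 / 800 pt-yr per arm; 800 is the plan's minimum.

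**2. Limits at low counts** (equal exposure T; the score interval takes its variance from the restricted maximum-likelihood estimate at each tested difference).

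- 0 v 0, Wald: 0 ± 1.96 × √0 = [0, 0] at any T.
- 0 v 0, score: at a difference δ > 0 the restricted rates are δ and 0, so √(δT) = 1.96 and δ = 3.84/T. This is ±0.32 / ±0.48 %/pt-yr.
- 1 v 0, Wald upper limit: (1 + 1.96)/T = 2.96/T = 0.24 / 0.37 %/pt-yr.
- 1 v 0, score upper limit: solve δT − 1.96√(δT) − 1 = 0, so √(δT) = (1.96 + √7.84)/2 = 2.38 and δ = 5.67/T = 0.47 / 0.71 %/pt-yr.
- Wald width as a share of score width: 46% at 1 v 0, 61% at 2 v 0, 83% at 5 v 0, 96% at 10 v 0.

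**3. Warfarin thrombosis rate** (protocol section 11, Table 3). Both events are in the high-risk PROACT controls.

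- All columns: 2/5,106.2 pt-yr = 0.039%/pt-yr.
- The three columns with target INR 2.0-3.0: 2/(1,360 + 1,090 + 343.5) = 2/2,793.5 = 0.072%/pt-yr.
- PROACT controls only: 2/(1,090 + 343.5) = 2/1,433.5 = 0.14%/pt-yr.

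**4. Frequency and coverage**, by exact Poisson enumeration. With equal rates λ, P(0 v 0) = exp(−2λT). For example, exp(−2 × 1,214 × 2/5,106.2) = 0.386. Sparse means 0 v 0, or one arm at zero with 1-5 events in the other.

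| Warfarin rate (%/pt-yr) | 0 v 0, equal rates | Sparse, equal rates | Wald coverage, apixaban 0.2% | Score coverage, apixaban 0.2% |
|---|---|---|---|---|
| 0.039 | 39% / 53% | 86% / 93% | 90.7% / 79.7% | 96.9% / 99.5% |
| 0.072 | 18% / 32% | 66% / 81% | 90.4% / 79.5% | 97.8% / 98.2% |
| 0.14 | 3% / 11% | 33% / 55% | 95.3% / 90.5% | 97.1% / 98.6% |

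The apixaban rate of 0.2%/pt-yr is an assumption. There, the Wald upper limit falls below the true excess in 9.1% / 20.2%, 9.1% / 20.2% and 3.9% / 8.7% of trials (nominal 2.5%). Misses in the other direction are below 1%. When both arms have the same rate, coverage is 96.5% or more for both methods, so the fault in that case is false precision rather than undercoverage.

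**5. Where the formula is adequate.**

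- Thromboembolism, 59/5,106.2 = 1.16%/pt-yr: Wald coverage 94.8-95.0% with an equal or doubled apixaban rate.
- Subgroups at 3.5 v 1.75%/pt-yr: 94.4-95.1% for shares of 20% to 50%; 94.9% / 92.3% at 10%; 87% / 87% at 5% (score 97% / 99%).
- Primary non-inferiority test at 1.75 v 3.50%/pt-yr: exact type I error 2.9% at 1,214 pt-yr, against 2.7% in the SAP's simulation.

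**The case against.** The strongest reply is that this is a textbook property of Wald intervals in one exploratory comparison that the SAP largely covers. The formula is labelled approximate, and the rate in each arm stands beside the interval. Section 5.2 lists the events concerned ("including valve thrombosis or dysfunction, stroke or TIA, myocardial infarction, arterial thromboembolism, bleeding") and section 6.4.2 says that they "will be summarized with frequencies and percentages per treatment group using the AT population". Anyone who sees no events in either arm will not read [0, 0] as proof of equality, and 6.1.1 allows a better method. Much of this stands, and it is why the severity is low. What it leaves open is the size of excess that can be excluded, which counts alone do not show. The 6.1.1 clause names neither a trigger nor an interval, so the choice would be made after the counts are known.

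A second reply is that the frequency depends on the warfarin rate. This also stands. A reader who takes only the pooled 0.039%/pt-yr, and pairs it with an apixaban rate of 0.1%/pt-yr, would infer that zero-width intervals are the usual result and that coverage is 81% / 67%. Two events cannot support that as the expected case. At 0.14%/pt-yr, 0 v 0 is uncommon and Wald coverage at 1,214 pt-yr is 94-95% for apixaban rates of 0.2-0.5%.

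Third, the subgroup case is thin. Clear failure appears only at an assumed 5% share with a doubled rate, and the documents do not show that any listed subgroup is that small.

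**Conclusion.** The point holds for valve thrombosis in 6.3.2. At 0 v 0 the planned interval carries no information, and at 1 v 0 it is less than half as wide as a score interval; the problem has faded by about 10 v 0. Those limits are arithmetic and need no rate assumption beyond the exposure. The frequency and coverage figures are conditional on the warfarin range of 0.039-0.14%/pt-yr, the assumed apixaban rate and 1,214 or 800 pt-yr per arm. SAP 6.1.3 records that the trial was stopped on safety grounds, and the documents do not give the final exposure; at a given rate, less exposure makes zero counts more likely.

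A reader might infer that the same formula undermines the primary non-inferiority result. The documents do not support that: about 21 events per arm are planned (0.0175 × 1,214), and at 21 v 21 the Wald upper limit is 96% of the score limit. Nor is there a general failure across subgroups. Severity is low, because no success criterion depends on these intervals.

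**What to change.** In 6.3.2, replace the cross-reference to 6.3.1 with a named interval for the rate difference that is valid at zero counts: a score interval of Miettinen-Nurminen type, or an exact one. In 6.7, use it only where a subgroup has zero or very few events in an arm. If results already exist, report it beside the planned interval. Leave the non-inferiority, OPC and log-rank rules as they are.

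The cost is two SAP sentences and a few lines of code, with no new data. There are two drawbacks. The score interval is conservative at very low counts (97-99.5% coverage in the 0.2%/pt-yr cases above), and in a 10% subgroup at 1,214 pt-yr it covers slightly less than Wald (93.9% v 94.9%). It would also be a late change, since v1.4 already records the stop, so the reason and date should be documented.
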